should be discontinued. If a patient discontinues due to respiratory AE, the Investigator should ensure that the patient has adequate evaluations as clinically indicated by a pulmonologist (consider PFTs, chest X-ray or high resolution computed tomography, based on findings of the other exams) at the time of the AE. For patients with pulmonary nodules, lung biopsy should be considered (Cryptococcus pneumonia and pulmonary TB have been reported with fingolimod). Further evaluations will be conducted until such time as resolution is confirmed or no further improvement is expected by the Investigator (based on a follow-up period of not less than 3 months).

- Hepatic effects
 - If patients have elevations in the LFTs (ALT or/and AST) ≥ 3 times the ULN, a retest should be performed as soon as possible but not later than 14 days after the original test. Upon confirmation of the abnormality, retests should be performed weekly until the elevated LFT decreases to below 3 times the ULN. At any time, if any of the following occur and there are no apparent alternative causes for the finding, the investigational drug must be permanently discontinued:
 - ALT or AST $> 8x$ ULN or
 - ALT or AST $> 5x$ ULN with confirmation, within 2 weeks or
 - ALT or AST $> 3x$ ULN and (total bilirubin $> 2x$ ULN) or
 - ALT or AST $> 3x$ ULN with the appearance of fatigue, nausea, vomiting, right upper quadrant pain or tenderness, fever, rash, and/or eosinophilia ($> 5\%$).

The Investigator should establish causality

After discontinuation due to elevation of ALT or AST $> 5x$ ULN or concurrent elevations of ALT or AST $> 3x$ ULN and bilirubin $> 2x$ ULN, further liver function evaluation should be performed (for example, coagulation panel and alkaline phosphatase) in consultation with the Medical Monitor.

- Macular edema
 - For patients with abnormal OCT findings or with visual signs or symptoms of new onset macular edema that develop following initiation of treatment, a general ophthalmologic examination including eye history, visual acuity, and dilated ophthalmoscopy will also be performed
 - Investigational drug must be discontinued in any patient who has a confirmed diagnosis of macular edema that is of new onset since Baseline
 - Patients with a diagnosis of macular edema must be followed up monthly and more frequently if needed based on the ophthalmologist's judgment

- Malignancies

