11.4. Clinical Laboratory Evaluations

Laboratory assessments will be performed by a central laboratory. All summaries will be based on the standard international (SI) units provided by the central lab. Each patient's hematology, blood chemistry, and urinalysis values will be flagged as "low", "normal", or "high" relative to the normal ranges of the central laboratory. Results from certain laboratory assessments are blinded as per Section 6.7.

Summary statistics of observed values, change and percent changes from Baseline in numeric laboratory parameters will be provided by visit (Baseline, Week 5 [hematology/chemistry/pregnancy only], Week 10, highest value post-baseline during IP, lowest value post-baseline during IP, last available measurement while on treatment during IP). For each laboratory parameter, frequency summaries of categorical shifts from Baseline to each post-Baseline time point (Week 5 [hematology/chemistry/pregnancy only], Week 10, and last available measurement while on treatment during IP) will be provided. For select laboratory parameters (ALC, ANC, WBC, AST, ALT), frequency summaries of patients with abnormalities will be summarized by visit (Baseline, Week 5 [hematology/chemistry/pregnancy only], Week 10, last available measurement while on treatment during IP) and overall.

All laboratory data will be listed, including unscheduled/repeat visits. Unscheduled visits will be included in the calculation of Baseline, highest/lowest/last available on treatment/anytime post-Baseline value.

For each laboratory test, individual patients with any values outside the standard reference range will have all their test results listed.

Hematology

The following laboratory parameters will be included in hematology summary tables: red blood cell (RBC) count, total and differential white blood cell (WBC) count (basophils, eosinophils, lymphocytes, monocytes, and neutrophils), platelet count, hemoglobin (HGB), hematocrit, mean corpuscular volume (MCV), mean corpuscular hemoglobin (MCH), and mean corpuscular hemoglobin concentration (MCHC).

The number and percentage of patients with abnormalities in hematology assessments, defined as $ALC < 200$ cells/ μ L, $ALC < 500$ cells/ μ L, $ANC < 1,000$ cells/ μ L, and total WBC $> 20,000$ cells/ μ L will be summarized overall and by visit post-Baseline. Patients with at least one abnormality in ALC, ANC or total WBC defined above will be listed.

Blood Chemistry

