The following laboratory parameters will be included in the blood chemistry summary tables at the screening visit: sodium, potassium, chloride, calcium, magnesium, phosphate, blood urea nitrogen (BUN), glucose, hemoglobin A1c, albumin, alkaline phosphatase, creatinine, alanine aminotransferase (ALT), aspartate aminotransferase (AST), gamma glutamyltransferase (GGT), total bilirubin, conjugated bilirubin, total cholesterol, triglycerides, high-density lipoprotein (HDL), low-density lipoprotein (LDL), and C-reactive protein (CRP). For all other visits the tests will include BUN, hemoglobin A1c, albumin, alkaline phosphatase, creatinine, ALT, AST, GGT, total bilirubin, conjugated bilirubin, and CRP.

The number and percentage of patients with abnormalities in ALT and AST, defined as $> 1 \times$ ULN, $\geq 2 \times$ ULN, $\geq 3 \times$ ULN, $\geq 4 \times$ ULN, $\geq 5 \times$ ULN, $\geq 8 \times$ ULN, and $\geq 10 \times$ ULN will be summarized by overall and by visit post-Baseline.

Patients with at least one ALT or AST that is $\geq 3 \times$ ULN will be listed showing all LFTs (ALT, AST, total bilirubin, direct bilirubin, alkaline phosphatase, and GGT) observed across all visits.

Evaluation of drug-induced serious hepatotoxicity (eDISH) plots of maximum ALT/AST values versus Total Bilirubin will be presented for assessment of potential Drug Induced Liver Injury (DILI). Total bilirubin value will be taken from the same visit at which maximum ALT/AST is observed. If maximum ALT/AST is reached at multiple visits, then the highest total bilirubin value from those visits will be plotted.

Urinalysis

The following laboratory parameters will be included for urinalysis: leukocytes, specific gravity, bilirubin, blood, glucose, ketones, pH, protein, and urobilinogen.

Serum pregnancy and serology testing

Serum β -human chorionic gonadotropin (hCG) will be collected at Screening for females of childbearing potential. Serology testing will also be collected at Screening and will include immunoglobulin G (IgG) antibodies to varicella-zoster virus (VZV), human immunodeficiency virus (HIV), immunoglobulin M (IgM) antibodies to hepatitis A virus (HAV), surface antigen of the hepatitis B virus (HBsAG), anti-hepatitis B core total antibodies (anti-HBc total), hepatitis B virus deoxyribonucleic acid (HBV DNA), and anti-hepatitis C virus (HCV) IgG/IgM.

Serum pregnancy results and serology testing results at Screening will be listed only.

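### The eDISH plot can show a concurrent ALT/AST and bilirubin elevation as an aminotransferase-only case when it falls only at a non-peak draw, and no visible by-arm table counts joint elevation

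*SAP*

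**What the plan says.** SAP 11.4 (Blood Chemistry) names the eDISH plot as the display for assessing potential drug-induced liver injury. The horizontal value is the patient's maximum ALT/AST. For the vertical value: "Total bilirubin value will be taken from the same visit at which maximum ALT/AST is observed". The one exception is a tie: "If maximum ALT/AST is reached at multiple visits, then the highest total bilirubin value from those visits will be plotted". The SAP gives no reference lines or quadrants, and does not say whether ALT and AST are combined or shown in separate panels.

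Protocol 12.2.6 (Hepatic effects) lists criteria introduced by "At any time, if any of the following occur and there are no apparent alternative causes for the finding". One of them is ALT or AST above 3x ULN together with total bilirubin above 2x ULN. After a first value of at least 3x ULN, "a retest should be performed as soon as possible but not later than 14 days after the original test". Once the elevation is confirmed, "retests should be performed weekly until the elevated LFT decreases to below 3 times the ULN".

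On repeat samples, SAP 11.4 states: "Unscheduled visits will be included in the calculation of Baseline". The same sentence extends this to the highest, lowest and last on-treatment values.

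The visible by-arm outputs that touch the liver are:

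- ALT and AST threshold counts. Bilirubin is not among the parameters counted: "For select laboratory parameters (ALC, ANC, WBC, AST, ALT), frequency summaries of patients with abnormalities will be summarized by visit".
- Summary statistics for each parameter, including the highest post-baseline value.
- Shifts, one parameter at a time: "frequency summaries of categorical shifts from Baseline to each post-Baseline time point".
- The adjudicated special-interest category for elevated ALT (SAP 11.2).
- Treatment-emergent adverse events leading to discontinuation (SAP 11.1).

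Separately, every patient with ALT or AST of at least 3x ULN is listed with all liver tests at all visits.

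**The concern.** The protocol's criterion can be met at any draw, and its retest rule generates draws on either side of a peak. The plot keeps only one draw per patient, the one where ALT/AST is highest. If bilirubin crosses 2x ULN before or after that draw while ALT or AST is still above 3x ULN, the plotted point does not show it.

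Hepatic effects are an adverse event of special interest, Protocol Appendix 3 lists liver injury as an important potential risk, and SAP 2 says these results are meant to be primary safety data for a marketing application. For a rare signal, one displaced patient can matter. A reader comparing arms on joint elevation would have to count points on the plot, because no visible table gives the number. Efficacy results are not involved.

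**Working it through.** The documents state no figure for this point, so there is none to reproduce. The check applies the two rules to the same data. Values are multiples of ULN. The joint region is defined here by the protocol's thresholds (above 3 and above 2), and the visit is read as one draw.

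**Step 1: constructed sequences (ALT/AST, bilirubin).**

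| Draw 1 | Draw 2 | Plotted point | Criterion met? | In joint region? |
|---|---|---|---|---|
| 4.5, 1.2 | 3.8, 2.4 | 4.5, 1.2 | yes | **no** |
| 3.5, 2.4 | 4.5, 1.5 | 4.5, 1.5 | yes | **no** |
| 6, 2.4 | 4, 2.6 | 6, 2.4 | yes | yes |
| 4.5, 2.4 | 3.8, 1.5 | 4.5, 2.4 | yes | yes |
| 3.5, 1.2 | 4.5, 2.4 | 4.5, 2.4 | yes | yes |
| 4.5, 1.2 | 4.5, 2.4 | 4.5, 2.4 (tie rule) | yes | yes |
| 4.5, 1.2 | 2.5, 2.4 | 4.5, 1.2 | no | no |

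Only the first two rows are misplaced. Both need a qualifying draw away from the peak and bilirubin of at most 2 at the peak.

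**Step 2: all two-draw sequences on a grid.** This tests logic, not frequency. ALT/AST takes 1, 2, 2.5, 3.5, 4.5 or 6; bilirubin takes 0.8, 1.2, 1.8, 2.4 or 3.0.

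- Each draw has 6 x 5 = 30 states, so there are 30 x 30 = 900 sequences.
- Qualifying states per draw: 3 x 2 = 6, leaving 24. Sequences meeting the criterion: 900 - 24 x 24 = 324.
- Sequences with a qualifying non-peak draw below a higher peak: 3 ALT pairs x 2 orders x 2 qualifying bilirubin values x 5 bilirubin values at the peak = 60.
- Plotted outside: 3 x 2 x 2 x 3 = 36 (18 with the qualifying draw before the peak, 18 after). The other 24 plot inside.
- Plotted inside without meeting the criterion: 0, because the plotted point is itself a real draw.

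**Step 3: separate panels.** Take (ALT 6, AST 3.2, bilirubin 1.0) then (ALT 4, AST 5, bilirubin 2.6). The ALT panel shows (6, 1.0), but the AST panel shows (5, 2.6), inside the region. With (6, 5, 1.0) then (4, 3.5, 2.6), both panels miss the patient.

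**Step 4: how many patients could be affected.** Protocol Appendix 3 gives 645 patients in Cohort 1 (2:1) and 367 in Cohort 2. It also gives, from the MS trials, 5.5% reaching at least 3x ULN, with a median time of 6 months (26 weeks). Carrying these over to UC is an assumption.

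- RPC1063 patients: 645 x 2/3 + 367 = 430 + 367 = 797. Expected at 3x ULN or more: 797 x 0.055 = 43.8.
- By Week 5: uniform onset up to the median, 43.8 x 0.5 x 5/26 = 4.2; exponential, 43.8 x (1 - 0.5^(5/26)) = 5.5.
- By Week 10: 8.4 and 10.3 by the same formulas. At most half can occur before the median, so 21.9 is a ceiling within this assumption only.
- Cohort 1 alone (430; 430 x 0.055 = 23.65): about 2 to 3 by Week 5, about 5 to 6 by Week 10, ceiling 11.8.

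After Day 1, Induction Period chemistry is scheduled at Weeks 5 and 10, and at Early Termination or Safety Follow-up where these apply, plus retests. Maintenance Period data fall under a separate SAP. A second elevated draw inside this analysis therefore comes mainly from an elevation found by Week 5. Only patients who also pass 2x ULN bilirubin at a non-peak draw, and not at the peak, would be misplaced. The documents give no rate for that.

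**The case against.** The strongest answer is that same-visit pairing is a reasonable choice. It keeps the two values concurrent, whereas plotting peak against peak would put patients who never met the criterion on one sample into the joint region. That stands, and it is why the fix leaves the pairing in place.

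A reader might infer that the SAP contradicts the protocol. It does not. The criterion in Protocol 12.2.6 is an individual discontinuation rule, conditional on there being no apparent alternative cause. The SAP sets no cut-offs for the plot, and Protocol 13.4.3 asks for no joint count.

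A reader might also infer that joint cases would vanish from the report. They would not. Anyone above 3x ULN is in the listing with bilirubin at every visit, and at the numbers above that listing is short enough to read by hand.

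Treatment-emergent events leading to discontinuation are tabulated by arm and may capture some of these patients. That holds only where the event is reported as an adverse event, and then under a system organ class and preferred term, so it is not a count of joint elevation.

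Finally, part of the plan is out of sight. Laboratory visits are assigned under Appendix 1.3, and SAP text is redacted. Either could hold a joint count or a visit definition that changes the result. If the visit means an analysis window, a retest may share it with the peak. The displacement could then disappear, or the paired values might come from different samples. This limits the finding to what is visible and to the same-draw reading.

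**Conclusion.** The point holds as a minor one. On the same-draw reading, the pairing rule can understate joint elevation and cannot overstate it. It does so only when the criterion is met solely at a non-peak draw and bilirubin at the peak is at most 2x ULN. It would be too strong to say that every patient who qualifies away from the peak is misplaced: 24 of the 60 such grid sequences plot correctly, and separate ALT and AST panels could rescue others.

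No visible by-arm output counts joint elevation. The patient-level information is complete in the listing, so the weakness is in the display and the between-arm comparison.

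Few patients are exposed and the number misplaced may be zero. Protocol Appendix 3 reports no severe drug-induced liver injury in the RMS, UC or CD trials as of 20 December 2018. The exposure figures depend on carrying the MS-trial rate and timing over to UC. No efficacy result is affected.

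**What to change.** Add to SAP 11.4 a count and percentage, by treatment/cohort, of patients with ALT or AST above 3x ULN and total bilirubin above 2x ULN on the same sample, at any post-baseline draw in the Induction Period, including unscheduled retests. Mark those patients on the eDISH plot, for example by also showing the qualifying draw. State whether the visit in the pairing rule means the same sample or the same analysis window, and whether ALT and AST are plotted together or separately.

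The cost is a few sentences of SAP text and minor programming on data already collected. The count may be zero in every group.

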11.5. Vital Sign Measurements

Systolic and diastolic blood pressure (SBP and DBP) and pulse (HR) will be assessed in a sitting position and collected at each visit. On Day 1 of treatment for the IP, careful cardiac monitoring of the patients is required. Resting pulse and blood pressure in the sitting position will be measured before the first dose of investigational drug and every hour for at least 6 hours thereafter. For the hourly measurements after investigational drug administration, HR and sitting blood pressure will be measured once and recorded in the eCRF. The first dose monitoring strategy should also be repeated at Day 5 or at Day 8 if any cardiac safety issues were observed on the previous Day of dose escalation.

Summary statistics of actual values and changes from Baseline in vital signs will be provided by visit (Baseline, Week 5, Week 10, highest value post-baseline during IP, lowest value post-baseline during IP, last available measurement while on treatment during IP). On Day 1, hourly

changes from predose up to hour 6 in blood pressures and HRs will be summarized for all patients.

Patient's lowest heart rate during 6-hour cardiac monitoring on Day 1 will be summarized by number and percentage by category: ≥ 65 , 60-64, 55-59, 50-54, 45-49, 40-44, 35-39, < 35 bpm, as well as < 40 bpm and < 45 bpm.

The number and percentage of patients requiring extended cardiac monitoring beyond hour 6 on Day 1 or requiring monitoring on Study Days 5 and/or 8 will be summarized by Day: Day 1, Day 5, and Day 8. A listing of these patients will be presented that shows the hourly change from the pre-dose assessment at each of the available Baseline, Study Day 5, and Study Day 8 visits by patient for HR and blood pressures.

The number and percentage of patients with clinically relevant abnormalities defined below will be summarized overall and by visit (Week 5, Week 10, last available while on treatment during IP) and overall. The denominator will be the number of patients with observed data at both Baseline and respective post-Baseline visit, unless specified otherwise.

- SBP:
 - > 140 mmHg post-Baseline
 - > 160 mmHg post-Baseline
 - > 180 mmHg post-Baseline or an increase from baseline of > 40 mmHg
 - > 180 mmHg post-Baseline (denominator will be the number of patients with Baseline SBP ≤ 180)
 - an increase from Baseline of > 40 mmHg
 - < 90 mmHg post-Baseline or a decrease from Baseline of > 30 mmHg
 - < 90 mmHg post-Baseline
 - < 90 mmHg post-Baseline (denominator will be the number of patients with Baseline SBP ≥ 90)
 - a decrease from Baseline of > 30 mmHg
- DBP:
 - > 90 mmHg post-Baseline
 - > 100 mmHg post-Baseline
 - > 105 mmHg post-Baseline or an increase from Baseline of > 30 mmHg

- >105 mmHg post-Baseline (denominator will be the number of patients with Baseline DBP \leq 105)
- an increase from Baseline of > 30 mmHg
- <50 mmHg post-Baseline or a decrease from Baseline of > 30 mmHg
 - <50 mmHg post-Baseline
 - <50 mmHg post-Baseline (denominator will be the number of patients with Baseline SBP \geq 50)
 - a decrease from baseline of > 30 mmHg
- HR:
 - >100 bpm post-Baseline
 - >120 bpm post-Baseline or an increase from baseline of > 20 bpm
 - >120 bpm post-Baseline (denominator will be the number of patients with Baseline HR \leq 120)
 - an increase from Baseline of > 20 bpm
 - <60 bpm post-Baseline
 - <45 bpm post-Baseline or a decrease from Baseline of > 20 bpm
 - <45 bpm post-Baseline (denominator will be the number of patients with Baseline HR \geq 45)
 - a decrease from Baseline of > 20 bpm

The number and percentage of patients with clinically relevant abnormalities during cardiac monitoring, including those beyond hour 6 on Day 1, will be summarized overall and by hour during pre-defined 6-hour monitoring window on Day 1, as well as overall during cardiac monitoring (Days 1/5/8). The denominator will be the number of patients with observed data at both Baseline and respective post-Baseline timepoint.

Discharge Status eCRF data after receiving extended cardiac monitoring after 6 hours will be summarized by number and percentage of patients. All data reported on the Discharge Status eCRF will be listed, including the reason for extended monitoring.

Box plots will be provided to display the distribution of vital signs results by timepoint on Day 1 up to hour 6, or by visit. In addition, line plots of means and SEs will be created to display the

actual values and change from pre-dose by timepoint on Day 1 up to hour 6. Line plots of means and SEs will also be created to display the actual values and change from Baseline by visit.

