If any of the following criteria are met, additional extended monitoring should be instituted until the finding has resolved. Baseline and hourly vital signs measurements (Hours 1 through 6) should be used to assess pulse (criteria 1 and 2 below) and ECG device results should only be used to assess for AV block and QTcF interval (criteria 3 and 4 below).

1. The pulse 6 hours postdose is < 45 bpm
2. The pulse 6 hours postdose is at the lowest value postdose and lower than any other timepoint (suggesting that the maximum PD effect on the heart may not yet have occurred), unless this value is greater than or equal to baseline
3. The ECG 6 hours postdose shows new onset second degree or higher AV block
4. For Adult patients, the ECG 6 hours postdose shows a prolonged QTcF interval (> 450 msec for males, > 470 msec for females)

Should postdose symptomatic bradycardia occur, the treating physician should be notified and he or she should initiate appropriate management, begin continuous ECG monitoring, and continue observation until the symptoms have resolved.

Should a patient require pharmacologic intervention for symptomatic bradycardia, continuous overnight ECG monitoring in a medical facility should be instituted, and the first dose monitoring strategy should be repeated the following day (Day 2). The first dose monitoring strategy should also be repeated at Day 5 or at Day 8 if any cardiac safety issues were observed on the previous Day of dose escalation (see [Table 2](#)).

Patients should have written instruction on when to return to the clinic and a 24-hour contact phone number to call in the event of any new or warranted symptoms (eg, chest pain, dizziness, palpitations, syncope, nausea, vomiting). Patients should be instructed not to drive on the same day after the first dose of investigational drug administration.

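### The SAP's table of lowest Day 1 heart rate stops at Hour 6, so its < 40 and < 35 bpm rows can be understated, and never overstated, for patients who are monitored longer

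*SAP*

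**What the plan says.** SAP 11.5 measures pulse before the first dose and then "every hour for at least 6 hours thereafter", so Day 1 readings after Hour 6 can exist. It then states that each patient's "lowest heart rate during 6-hour cardiac monitoring on Day 1 will be summarized by number and percentage by category". The categories are 5-bpm bands running from 65 and above to below 35, "as well as < 40 bpm and < 45 bpm".

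Protocol 12.1.10 lists four Hour 6 findings, and if any is met, "additional extended monitoring should be instituted until the finding has resolved". Two concern pulse:
- "The pulse 6 hours postdose is < 45 bpm"
- "The pulse 6 hours postdose is at the lowest value postdose and lower than any other timepoint". The protocol gives its reason: "suggesting that the maximum PD effect on the heart may not yet have occurred". It exempts patients whose Hour 6 pulse is at or above baseline.

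The other two are new second-degree or higher AV block and a prolonged QTcF.

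Elsewhere in SAP 11.5, "clinically relevant abnormalities during cardiac monitoring, including those beyond hour 6 on Day 1" are summarized. The low heart-rate limits defined in that section are < 60 bpm, < 45 bpm and a fall of more than 20 bpm. The section also counts patients who need extended monitoring, lists their hourly changes, and reports the Discharge Status data with the reason for extension.

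**The concern.** The lowest-rate table is the only visible output with rows for < 40 and < 35 bpm. For a patient kept because the Hour 6 value is the lowest so far, the table records that value and ignores what the extra observation found. The protocol treats bradycardia as an adverse event of special interest (12.2.6). Its benefit-risk appendix relies on the absence of rates below 40 bpm in the multiple sclerosis trials. A reader will look to the same row here, and it should not omit readings already taken without saying so.

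**Working it through.** The plan states no figure on this point, so there is none to reproduce. The check compares the outputs and reasons about direction.

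**1. Is the window really fixed at Hour 6?** Yes, on the natural reading. Where SAP 11.5 wants later readings it says so ("clinically relevant abnormalities during cardiac monitoring, including those beyond hour 6 on Day 1"). The lowest-rate sentence has no such phrase and names the 6-hour period.

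**2. Which visible heart-rate outputs use readings after Hour 6?**

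| Output in SAP 11.5 | Uses Day 1 readings after Hour 6? | Gives a count below 40 or 35 bpm? |
|---|---|---|
| Lowest Day 1 heart rate, by category | No | Yes |
| Hourly change summaries, Day 1 box and line plots | No (to Hour 6) | No |
| Abnormalities during cardiac monitoring | Yes | No (< 60, < 45, fall > 20) |
| Lowest post-baseline value during induction | Not stated | No (summary statistics) |
| Listing of patients with extended or repeat monitoring | Yes, on the natural reading | No (hourly changes by patient) |

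No row has Yes in both columns.

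**3. Direction of the error.** For one patient, let A be the Hour 1-6 readings and B all Day 1 postdose readings. Every reading in A is also in B, so min(B) ≤ min(A). For any cut-off c, the number of patients with min(B) < c is therefore at least the number with min(A) < c. This fixes the direction for the cumulative rows < 40 and < 35 within each treatment group. It does not fix the direction for a closed band such as 35-39, which patients can both enter and leave. Nor does it fix the direction of the difference between groups, since placebo patients can also be kept longer.

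**4. Who is affected?**
- *Hour 6 pulse the lowest so far:* the recorded minimum is the Hour 6 value, and the Day 1 minimum is equal or lower.
- *Hour 6 pulse < 45 bpm:* the patient is already in the < 45 row, so only the depth below that can be missed.
- *AV block or QTcF:* later pulse readings are left out too, whatever the pulse was at Hour 6.

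**5. Illustration (values invented).** With 46 bpm at Hour 6 as the in-window minimum and 38 bpm at Hour 8, the lowest-rate table shows 45-49 bpm. Over all readings the band would be 35-39. If baseline is 45 bpm or more, the abnormality summary counts the patient as < 45. Nothing visible counts the patient as < 40.

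**6. Size.** A row changes only if a patient is kept, has an in-window minimum at or above the cut-off, and later reads below it. Resting rate below 55 bpm at Screening is an exclusion. From 55 bpm, a reading below 40 needs a fall of more than 55 − 40 = 15 bpm, and one below 35 a fall of more than 55 − 35 = 20 bpm. The Screening rate is not the predose baseline, which may be lower, so this is only a guide. Protocol Appendix 3 reports, from multiple sclerosis trials at the same 0.23 mg first dose, a greatest mean reduction of 1.2 bpm at Hour 5, near baseline at Hour 6. Few such patients are to be expected. The documents give neither the number kept longer nor the distribution of later rates, so a numerical estimate would rest on invented inputs.

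**The case against.** **An equal window is a legitimate choice.** Each patient has the same six scheduled readings, so the groups are compared on the same footing. Adding readings only for patients already selected on their Hour 6 result lowers their minimum partly by chance and makes ascertainment depend on outcome. This stands, and it is why the Hour 1-6 version must stay. It does not argue against showing the second version beside it with a label.

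**The later readings are already reported.** This stands in large part. A reader might infer that the SAP discards readings after Hour 6. It does not: the abnormality counts and the patient listing use them. Only the counts below 40 and 35 bpm are missing.

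**Late minima are unlikely.** The Appendix 3 profile points to a mean low at Hour 5, not later. That is a mean in another disease and does not exclude individual late minima, but it gives no support for a material understatement.

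Two other inferences also fail. The affected patients are not exactly those with a possible late minimum, because patients kept for pulse < 45 bpm, AV block or QTcF are affected too. And different < 45 counts in the two tables would not show an error. The abnormality summary also covers Days 5 and 8, and it requires observed data at both baseline and the timepoint. The general definition of < 45 also restricts the denominator to patients with baseline heart rate of at least 45 bpm.

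**Conclusion.** The point holds as a minor reporting gap. The < 40 and < 35 bpm rows leave out Day 1 readings after Hour 6, no other visible summary supplies those counts, and the omission can only lower them. The expected effect is very small and no magnitude should be attached to it. A reader might infer that first-dose bradycardia will be materially under-reported, or that the monitoring itself is deficient; the documents support neither.

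The conclusion assumes that the 6-hour wording means Hours 1 to 6, that the monitoring abnormalities use the heart-rate limits defined just above them in SAP 11.5, and that no redacted or removed text already supplies the missing counts. Efficacy results are untouched.

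**What to change.** Keep the Hour 1-6 table as it is. Beside it, add a column with the lowest heart rate over all Day 1 postdose readings, including extended monitoring, in the same categories.

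Alternatively, add < 40 and < 35 bpm rows to the abnormality summary that already includes readings beyond Hour 6. In that case, state which of its overall rows contains the later Day 1 readings, since one of them pools Days 1, 5 and 8.

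Either way, add a footnote that patients with extended monitoring contribute more readings, and that the windows and denominators of the two tables differ, so their < 45 counts need not match.

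The cost is a sentence or two of SAP wording and a little programming on data already collected. The drawback is the unequal number of readings, which the retained Hour 1-6 column and the footnote address. No monitoring rule changes.
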